8.7 Analysis of Safety

Safety population will be used for the analysis of Safety.

Safety data will be displayed by (i) dose group and BW stratum and (ii) by all BW strata combined for STP206 low dose, STP206 high dose and control group.

8.7.1 Extent of Exposure and Compliance to Study Treatment

All exposure summaries will be presented by the safety population.

The extent of subject exposure to study treatment will be quantified using the parameters of total cumulative dose [redacted], Average daily dose, and duration of dosing. Total cumulative dose is defined as the actual cumulative dose of study treatment received during the entire dosing period. The average daily dose is defined as total cumulative dose divided by number of days elapsed from first dose to last dose, and the duration of dosing is defined as the total number of dosing days, in which a subject is actually receiving study treatment.

Total cumulative dose will be summarized using descriptive statistics (number of subjects [N], mean, standard deviation [SD], median, 25th and 75th quartiles, minimum [min], and maximum [max]). Average daily dose [redacted] will be summarized by descriptive statistics (number of subjects [N], mean, standard deviation [SD], median, minimum [min], and maximum [max]). The duration of dosing (days) will be summarized using descriptive statistics (number of subjects [N], mean, standard deviation [SD], median, minimum [min], and maximum [max]).

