### **6.2. Objectives**

#### **6.2.1. Primary Objective**

The primary objective of the study is to assess the safety and tolerability of once-daily dosing of two dose levels of STP206 versus control in four different birth weight strata in premature neonates.

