### **6.3. Endpoints**

#### **6.3.1. Primary Endpoints**

The incidence and severity of AEs, SAEs and changes in clinical parameters in STP206-treated subjects compared to control subjects from baseline through 30 days after the last dose of blinded study treatment.

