## **10.8. Study Medication Administration and Compliance**

### 10.8.1. Dosage and Administration

Dosing of blinded study drug will be initiated within 4 days (i.e., 96 hours) after birth. Dosing is intended to consist of a single daily bolus dose administered as part of a scheduled feeding. However, in neonates who are volume restricted, the total daily dose may be divided and given twice daily (BID) or three times daily (TID) until full amount can be tolerated in one dose. In neonates where the dose volume is less than the maximum volume tolerated, dosing may be supplemented with regular feeding. In neonates receiving continuous feeds, the feed will be interrupted for dose administration and then immediately restarted. The date, time and volume of each dose administration will be recorded.

In neonates who are still on tube feeds, the dose will be given by feeding tube prior to feeding. If dosing at the time of feeding is not possible, the dose may be given and then the line flushed with sterile water to assure delivery of the full dose. In larger neonates who feed orally by breast or bottle for all feeds and do not have a feeding tube in place, the dose will be fed directly into the mouth before a feed using a syringe intended for oral drug administration. In the event the dose is spit up, the neonate will not be re-dosed. Regurgitation of the dose will be noted in the source document and the case report form.

Prior to administration, subject identification will be verified against the labeled syringes to ensure that the correct IP is given.

The times of product reconstitution and dose administration will be recorded. Reconstituted components of STP206 should be administered within 2 hours following reconstitution.

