### 10.8.2. Suspension of Study Drug Administration

Study drug administration will be suspended temporarily in subjects with a case of suspected sepsis (see [Section 10.3.5.1](#)) or infection of a normally sterile site (see [Section 10.3.5.2](#)). Study drug may be re-initiated at the discretion of the Investigator, if the subject's clinical condition permits and:

- Cultures are negative for gram positive bacilli or,

- STP-206 organisms are not confirmed by central laboratory analysis.

Additionally, dosing of blinded study treatment may be withheld at the discretion of the physician Investigator. The reason for suspension of blinded study treatment will be documented in the subject's source documents and the case report form.

Neonates will be discontinued from the study if:

- Dosing is suspended for greater than seven consecutive days or
- More than two suspensions of oral dosing of five or more consecutive days each in duration are required.

If the neonate is placed on NPO status for suspected NEC and the NPO status is maintained for greater than 24 hours, dosing of blinded study drug will be suspended until NPO status is removed.

If NEC is diagnosed, study drug administration will be immediately discontinued.

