### 11.3.2. Dosing Duration

The subject’s gestational age at birth will dictate how many weeks of dosing will be administered as outlined in the table below. For the initial 2 weeks of daily dosing, neonates should not miss more than 2 doses per week. It is intended that neonates receive blinded study treatment for between 2 to 11 weeks based upon the protocol-defined gestational age. However, in the event of early hospital discharge, the minimum required dosing duration is provided in [Table 2](#).

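### No tolerability measure is designated, and no exposure parameter in SAP 8.7.1 relates dosing received to the infant's own intended 14 to 77 days

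*SAP*

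**What the plan says.** - Protocol 6.2.1: "The primary objective of the study is to assess the safety and tolerability of once-daily dosing of two dose levels of STP206 versus control". Protocol 6.3.1 gives the primary endpoint: "The incidence and severity of AEs, SAEs and changes in clinical parameters in STP206-treated subjects compared to control subjects from baseline through 30 days". Neither document labels any endpoint, variable or criterion as tolerability.
- Protocol 11.3.2: "gestational age at birth will dictate how many weeks of dosing will be administered". Table 2 sets 77 intended days at 23 weeks, falling by a week per gestational week to 14 days at 32 weeks, with a minimum number of cumulative dosing days for each row. SAP 6.2.3 repeats the table.
- SAP 8.7.1 quantifies exposure by cumulative dose, "Average daily dose, and duration of dosing". Average daily dose is cumulative dose over the days from first to last dose. For duration, "the duration of dosing is defined as the total number of dosing days, in which a subject is actually receiving study treatment". SAP 8.7 shows safety data by dose group and birth weight stratum, and for all strata combined.
- Protocol 10.8.1 allows the daily dose to be divided in volume-restricted infants and requires the date, time and volume of each administration. It adds: "Regurgitation of the dose will be noted in the source document and the case report form". On suspensions, Protocol 10.8.2 says: "The reason for suspension of blinded study treatment will be documented", in the source documents and the case report form.

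**The concern.** The SAP section has compliance in its title but contains no compliance measure. A count of dosing days cannot distinguish an infant born at 23 weeks who stopped for good after two weeks from one born at 32 weeks who finished the course. Yet tolerability is a primary question, and Protocol 7.1 makes further use of the high dose depend on its being well tolerated. The daily volume is 0.2 mL at the low dose and 1.8 mL at the high dose (Protocol 8.4.1), so whether the volume is tolerated is itself a dose-level question. The records that bear on it most directly are suspensions with reasons, divided doses and regurgitated doses. None of the planned table titles in SAP section 11 names them.

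**Working it through.** **1. Reproduce the plan's table.** Intended days = (34 − completed weeks) × 7: (34 − 23) × 7 = 77 and (34 − 32) × 7 = 14. Minimum days = 0.70 × intended, rounded up: 53.9 → 54 and 9.8 → 10. All ten rows of Table 2 match. With 0.75, the figure in the SAP 6.2.3 footnote, the results are 57.75 → 58 and 10.5 → 11, and no row matches.

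**2. Raw days against percent of intent.**
- 14 days received: 14/14 = 100% at 32 weeks; 14/77 = 18% at 23 weeks.
- 30 days received: 30/42 = 71% at 28 weeks, which reaches the minimum of 30; 30/77 = 39% at 23 weeks, where the minimum is 54.

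Duration as defined in the SAP scores each pair as equal.

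**3. Average daily dose.** Its denominator ends at the last dose. It falls when doses are missed mid-course. A 23-week infant given every dose and stopped for good on day 14 still scores 100% of nominal.

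**4. Share of variance of raw days explained by intended days.** Gestational ages possible in each stratum come from the 10th-90th percentile weights in Protocol Appendix D:

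| Stratum | Weeks | Intended days |
|---|---|---|
| 2000-1501 g | 29-32 | 14-35 |
| 1500-1000 g | 26-32 | 14-56 |
| 999-750 g | 24-29 | 35-70 |
| 749-500 g | 23-27 | 49-77 |

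Assumptions, since the documents give no such figures: days received = intended × a Beta-distributed fraction independent of gestational age; strata of equal size; gestational-age mix either even over the possible weeks or weighted by normal weight curves fitted to Appendix D. The share is the squared correlation of days received with intended days. Ranges span the two mixes.

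| Fraction received, mean (SD) | All strata combined |
|---|---|
| 0.95 (0.05) | 98% |
| 0.90 (0.10) | 93% |
| 0.85 (0.15) | 83-85% |
| 0.80 (0.20) | 71-74% |
| 0.75 (0.25) | 58-61% |

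Within strata, heaviest to lightest: at 0.90 (0.10), 86-88%, 85-92%, 64-80% and 42-66%; at 0.80 (0.20), 55-60%, 52-69%, 25-44% and 13-28%.

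**5. Chance imbalance within a cohort.** Twelve infants at 2:1 gives 8 v 4. With perfect adherence, the 95% range of the arm difference in mean days is 1.96 × SD × √(1/8 + 1/4) = 1.96 × 0.612 × SD.

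| Stratum | Mix | SD of intended days | 95% range |
|---|---|---|---|
| 1500-1000 g | even | 14.0 | ±16.8 |
| 1500-1000 g | weighted, infants above the 90th percentile included | 10.3 | ±12.4 |
| 1500-1000 g | weighted, 10th-90th percentile only | 9.5 | ±11.4 |
| 749-500 g | even | 9.9 | ±11.9 |
| 749-500 g | weighted | 6.7 | ±8.1 |

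**6. The same for the combined arms.** Each dose arm and the pooled control have 8 infants per stratum, 32 v 32. Variance = (1/16) × ΣSD² × (1/8 + 1/8). With the even mix the SDs are 7.8, 14.0, 12.0 and 9.9, so ΣSD² ≈ 498, variance ≈ 7.8 and the range is 1.96 × 2.79 = ±5.5 days. With weighted mixes it is about ±4.

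**The case against.** The strongest reply is that the plan already measures tolerability without using the word. Protocol 7.1.3.1 defines treatment discontinuation as not completing treatment through 34 weeks post-conceptual age or discharge, which is relative to each infant's own course, and SAP section 11 plans end-of-treatment disposition tables by stratum and combined. AEs leading to discontinuation, Grade 3 and related AEs, and feeding intolerance are also tabulated. Average daily dose picks up mid-course gaps. Exposure is shown by stratum, and randomisation within each cohort balances gestational age in expectation. The trial is descriptive throughout.

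Much of this stands. A reader might infer that the trial could say nothing about whether either dose was tolerated; the outputs just listed rule that out. A reader might also infer that every duration summary mostly shows gestational age. That holds for the combined table under every assumption tried, but not in the two lightest strata once adherence drops, and in the combined arm comparison chance imbalance is only about ±4 to 5.5 days. Nor can one say that the dosing records go unused: listing 16.2.5 covers study drug exposure, and the table shells are in a separate document not available here.

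The existing outputs still leave a gap. Complications of prematurity are not AEs (Protocol 10.3.5 and 12.3.1) and NEC is among them (10.5.2.1), so a stop for NEC can fall outside the table of AEs leading to discontinuation. Temporary suspensions are not discontinuations. Disposition does not show missed, divided or regurgitated doses. Feeding intolerance is an efficacy variable about feeds. A listing is not a summary by arm.

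**Conclusion.** The point holds in a limited form. No tolerability measure is designated for the primary objective, and no exposure parameter defined in SAP 8.7.1 relates dosing received to dosing intended. The all-strata summary of raw days mainly reflects gestational age (58-98% of variance); within strata this depends on adherence and is weakest in the two lightest. In the two strata worked in step 5, a single-cohort arm difference of one to two weeks in mean dosing days could arise from gestational-age imbalance alone. These sizes rest on the assumed gestational-age mix and adherence, which the documents do not supply. The example of 100% against 18%, and the blindness of average daily dose to permanent early stops, need no assumption. Because the data needed are largely recorded already, this is an inexpensive change that should be made.

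**What to change.** In SAP 8.7.1 add one table, by arm and cohort and for all strata combined:

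- dosing days received as a percentage of the infant's Table 2 intended days, with the reason for any shortfall, so that early discharge is not read as intolerance;
- percent reaching the minimum dosing days;
- percent with any dosing suspension, by reason;
- percent with divided dosing, derived from recorded dose times and volumes, since the protocol names no separate field for it;
- percent of doses regurgitated.

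Name these, together with treatment discontinuations, as the descriptive tolerability measures for the primary objective. Cumulative dose without regurgitated doses is optional.

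Before reporting percent reaching the minimum, reconcile the 70% footnote to Protocol Table 2 with the 75% footnote in SAP 6.2.3; the day counts, identical in both, match only 70%. Also correct SAP 8.3.3, which cites Protocol 11.2.3 (intraventricular hemorrhage) for the minimum days; they are in 11.3.2.

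Cost: SAP wording and one table. Regurgitation and reasons for suspension are already on the case report form, and the date, time and volume of each dose are recorded.

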8.7.2 Adverse Events

All AE summaries will be presented by the safety population.

All AE tables will include only treatment emergent AEs (TEAEs) unless otherwise noted. TEAEs are those which start or worsen in severity after the first dose of study medication. If it

cannot be determined if the AE started or worsened after the first dose of study treatment, it will be assumed to be a TEAE.

AEs will be assessed from the time the subject receives their initial dose of study medication up to 6 months following the last dose of study drug (note that some sites used 6 months gestational age rather than 6 months post last dose). All AEs reported during this period, regardless of severity relationship to blinded study treatment, will be recorded. The investigator's verbatim term of each adverse event will be mapped to the system organ class and preferred term using the MedDRA dictionary.

All AE tables will be summarized for each treatment group by system organ class (SOC) and preferred term (PT) using counts and percentages.

In order to count the number of subjects who experienced each AE, a subject experiencing the same AE multiple times will only be counted once for the corresponding preferred term. Similarly, if a subject experienced multiple AEs within the same SOC, that subject will be counted only once for that SOC. Adverse events will be presented in alphabetical order of SOC and within each SOC, in decreasing order of the total number of subjects who experienced each AE at the preferred term level.

Adverse events will also be presented by severity for Mild AE (Grade 1), Moderate AE (Grade 2) and Severe AE (Grade 3). In the case of multiple experiences with the same AE, the subject will be counted only once under the worst reported severity. Missing category will be presented to summarize any missing severity.

Serious adverse events (SAEs) will be presented by SOC and preferred term.

Adverse events will also be summarized by relationship. Treatment related AEs include those events that were rated by the investigator as possible or probable related. Missing category will be presented to summarize any missing relationship.

The following AE categories will be summarized:

- Overall AE summary
- AEs by SOC and preferred term
- Related AEs by SOC and preferred term
- Grade 3 AEs by SOC, preferred term and relationship to study treatment
- Treatment Related AEs with Grade 3 by SOC, preferred term
- AEs leading to discontinuation of study treatment by SOC, preferred term
- AEs leading to death by SOC, preferred term
- SAEs by SOC, preferred term

Additionally, the following listings will be produced:

- All AEs
- All SAEs
- AEs that resulted in discontinuation of study treatment
- AEs with an outcome of death

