#### **6.3.2. Secondary Endpoints**

The secondary endpoints of the study are:

- The incidence and the severity of AEs and SAEs in STP206-treated subjects compared to control subjects from baseline through six months after the last dose of blinded study treatment
- The incidence of clinical events (NEC, sepsis/bacteremia, feeding intolerance, death, morbidity/complications of prematurity) in STP206-treated subjects compared to control subjects from baseline through hospital discharge
- The assessment of the fecal shedding of STP206 organisms in STP206-treated subjects compared to its baseline and to control subjects through the last dose of blinded study treatment

- The assessment of the changes in routine clinical parameters in STP206-treated subjects compared to control subjects at baseline through the last dose of blinded study treatment
- The assessment of the progression of standard neonatal growth parameters in STP206-treated subjects compared to control subjects through the 6-month postdosing visit.

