#### *11.3.3.4. 6 Months/End of Study*

The following procedures will be performed between 181 and 195 days following completion of dosing:

- Physical Examination
- Vital Signs
- Growth Assessment
- Assessment of AEs
- Assessment of concomitant medication changes

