## 12. ADVERSE EVENTS

### 12.1. Assessment Period

AEs will be assessed from the time the subject receives their initial dose of study medication through 6 months following the last dose of study drug. All AEs reported during this period, regardless of severity relationship to blinded study treatment, will be recorded.

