Post Dosing 6 Month ^d	181 to 195 days	181 <= (assessment date – expected last dose date+1) <= 195 days
Post Dosing 18 Month/End ^d	Not specified	520 <= (assessment date – expected last dose date+1) <= 576 days
Withdrawal Prior to Post Dosing 6 Month ^d	Not specified	assessment date >= date of withdrawal and (assessment date – expected last dose date+1) <= 181 days
Withdrawal between Post Dosing 6 and 18 Month ^d	Not specified	assessment date >= date of withdrawal and 196 days < (assessment date – expected last dose date+1) < 520 days

- a- Windows for vital sign measurements and physical examinations.
- b- Window for fecal sample.
- c- Window for IVH measurement.
- d- Windows for growth assessment (note that Post Dosing 18 Month data will only be presented in listings).
- e- Windows for Post Dosing may be adjusted to account for patients that terminated dosing early. For example, if a subject early terminates dosing at Week 10 but was expected to complete dosing at Week 11, then the Post Dosing window will be adjusted to reflect planned time point after expected dosing completion.

If a subject has more than 1 assessment occurring in the same visit window, the data from the visit closest to the scheduled study day will be used for summaries. If two assessments have the same distance from the scheduled study day, the assessment after the scheduled study day will be used for the analyses.

If multiple assessments occur as Baseline (screening or Day 1 prior to dosing), then the last assessment before the first study dose will be used for the analyses.

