6.6 Safety Assessments

The following are the safety assessments:

- The incidence and severity of adverse events, serious adverse events, and changes in clinical parameters from baseline through six months after the last dose of blinded study treatment.
- Physical examination through six months after the last dose of the study treatment.
- Vital signs evaluation through six months after the last dose of the study treatment.
- Concomitant medications evaluations for infant through six months after the last dose of the study treatment.
- The assessment of the progression of standard neonatal growth parameters (head circumference, body length, and body weight) in STP206-treated subjects compared to control subjects through 60f corrected age.
- Number and percent of subjects with presence of STP206 organisms in fecal shedding in STP206-treated subjects compared to control subjects through the last dose of blinded study treatment

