8 STATISTICAL ANALYSIS

All statistical analyses will be performed using SAS® (version 9.4 or higher).

Unless otherwise noted, summary tables will only include data up to the Month 6 Post-Dose visit. Data collected after that will only be included in listings.

Safety and efficacy data will be summarized using BW strata. If deemed necessary, additional analyses may be conducted on pooled data across cohorts, where incidence of clinical events

(NEC, sepsis, feeding intolerance, death, morbidity/complications of prematurity) may be presented.

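### The SAP notes that some sites timed six-month follow-up from a different anchor but sets no rule for them, so six-month AE/SAE incidence may mix follow-up lengths and, if the visit moved too, growth data could drop out of the six-month table

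*SAP*

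**What the plan says.** Protocol 6.3.2 defines a secondary AE/SAE endpoint "from baseline through six months after the last dose of blinded study treatment" and a growth endpoint that runs to the six-month post-dosing visit. Protocol 12.1 sets the same AE period. Protocol 11.3.3.4 places AE and growth assessment at one visit, "between 181 and 195 days following completion of dosing".

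SAP 8.7.2 repeats the six-month AE period and then adds in parentheses: "note that some sites used 6 months gestational age rather than 6 months post last dose". It does not say which sites, how many infants, or what the phrase means once a child is born. SAP 6.6 describes growth "compared to control subjects through 60f corrected age". That text is garbled, but it points to an age-based anchor and not to the post-dosing visit.

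On the analysis side:

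- SAP 6.2.2, Table 4, accepts a six-month growth assessment only if "181 <= (assessment date – expected last dose date+1) <= 195 days". Its footnote e allows windows to shift for early end of dosing and for nothing else.
- SAP 7.5 pools all sites.
- SAP 8 says that "summary tables will only include data up to the Month 6 Post-Dose visit", unless otherwise noted.
- SAP 8.7.2 defines treatment-emergent AEs by a start but no end day, and reports counts and percentages.
- SAP 8.7.1 summarises exposure to dosing, not follow-up time.
- SAP 5.1 and 5.2, which record changes in conduct and analysis, do not mention the different anchor.

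**The concern.** A crude six-month percentage is interpretable only if infants were watched for about the same time. The SAP records that at some sites they may not have been, and gives no common cut-off, site flag, follow-up summary or sensitivity analysis.

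Randomisation is stratified by birth weight and not by site. Each of the eight groups has about 12 infants at 2:1, so about 8 against 4, and the groups open one after another. Low dose, high dose and control can therefore differ in site mix, and with it in follow-up, by chance.

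For growth, the risk is that an infant who was measured and completed the study would contribute nothing to the six-month table because the visit date fits no scheduled window.

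**Working it through.** **1. Which clock the protocol intends.** Dosing lasts 14 to 77 days (Protocol Table 2) and the final visit is 181 to 195 days later. Participation is then (14 + 181)/7 = 27.9 weeks to (77 + 195)/7 = 38.9 weeks, which reproduces the 28 to 39 weeks in Protocol 7.4.1. Counted from birth, a final visit at six months corrected age would give (280 + 182.6 − 230)/7 = 33.2 to (280 + 182.6 − 161)/7 = 43.1 weeks. A visit at six months chronological age would give 182.6/7 = 26.1 weeks for everyone. Only the post-last-dose clock matches the protocol's figure.

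**2. Where a shifted visit would land.** Inputs:

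- Gestational age at birth is 23w0d to 32w6d (161 to 230 days; Protocol 9.2 and Table 2).
- Dosing starts on day 0 to 4 of life (Protocol 10.8.1).
- Six months is taken as 365.25/2 = 182.6 days, and term as 40 weeks = 280 days (assumptions).
- SAP day = assessment date − expected last dose date + 1 (SAP Table 4).

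The expected last dose was set two ways: at exactly 34w0d (238 days), or at first dose + intended dosing days − 1.

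| Reading | Expected last dose | SAP day of an on-target visit |
|---|---|---|
| Corrected age | 34w0d | 280 + 182.6 − 238 + 1 = 225.6 |
| Corrected age | First dose + intended days − 1 | 217 to 227 |
| Chronological age | 34w0d | 161 + 182.6 − 238 + 1 = 106.6 (23w0d) to 230 + 182.6 − 238 + 1 = 175.6 (32w6d) |
| Chronological age | First dose + intended days − 1 | 104 (23 weeks) to 171 (32 weeks) |

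**3. Against the windows.** Days 217 to 227 are 22 to 32 days past the upper limit (217 − 195; 227 − 195). Days 104 to 176 are 5 to 77 days short of the lower limit (181 − 176; 181 − 104). The neighbouring scheduled windows are three months (days 85 to 99) and 18 months (days 520 to 576, listings only). Withdrawal windows cover the gaps, but they apply only to infants who withdrew. No eligible gestational age puts an on-target visit inside days 181 to 195 under either reading.

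**4. AE follow-up length.** Against a compliant visit at days 181 to 195, the corrected-age reading gives about 11% to 25% more post-dose follow-up (217/195 = 1.11; 227/181 = 1.25). The chronological reading gives 5 to 91 days less (181 − 176; 195 − 104).

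**The case against.** The strongest reply has four parts.

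*The note concerns AEs only.* A reader might infer that growth visits at these sites did miss the window and that whole sites will vanish from the table. The documents do not say so. The shared visit in Protocol 11.3.3.4 makes a shift likely, and the garbled line in SAP 6.6 is weak support, but neither gives dates or site counts. A visit made 22 to 32 days early (corrected age), or only 5 days late for the most mature infants (chronological age), would still reach the window. The growth claim must therefore stay conditional.

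*The AE cut-off may already exist.* SAP 8.7.2 describes a period of up to six months after the last dose, and SAP 8 sends later data to listings. If the Month 6 visit means Table 4's days 181 to 195, late events are already excluded. That reading is possible, but it is not written as a rule, and it does nothing for sites that stopped early.

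*The impact is limited.* The primary endpoint runs "from baseline through 30 days after the last dose of blinded study treatment", and NEC, sepsis, death and other clinical events are counted through discharge. All comparisons are exploratory (SAP 7.1), randomisation is central and assessors are blinded. It would be wrong to infer that the main safety result is compromised or that an arm is systematically favoured. This stands in full.

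*Deviations are already logged* under Protocol 14.1.2, SAP 8.2 and Listing 16.2.2.2. True, but logging does not tell the programmer how to count the events or place the visit.

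**Conclusion.** The point holds in a limited form. The SAP acknowledges a different follow-up anchor at some sites and gives no explicit rule for it. Six-month AE/SAE incidence may therefore rest on unequal follow-up. If the shared visit moved as well, on-target growth assessments at those sites fall at about day 217 to 227 or 104 to 176 and leave the six-month summary.

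The direction is unknown, because the anchor is undefined: follow-up is longer under corrected age and shorter under chronological age. The number of sites is unknown too. The day ranges assume dosing to 34w0d or for the full intended duration, and visits on target. Only the six-month AE/SAE and growth secondary summaries are touched. No alpha or power figure is involved.

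**What to change.** 1. Define the anchor used at those sites, and flag the affected sites and infants in the listings.
2. State one AE onset cut-off, counted from last dose, and apply it to every infant in the six-month AE/SAE tables. It should agree with the protocol's visit window, for example the earlier of the six-month visit and day 195. A cut at day 182 would push events from days 183 to 195 at compliant sites into listings, although the protocol permits the visit until day 195. Say whether the count uses the actual or the expected last dose, and whether it includes Table 4's added day.
3. Show follow-up time by arm. Where follow-up was shorter, add incidence per infant-month beside the crude percentage.
4. Assign the final growth visit by its nominal CRF label, or add a window that captures it. Classify the measurement at the infant's actual age, and give a sensitivity table restricted to days 181 to 195.
5. Correct the growth text in SAP 6.6 to match the protocol's six-month post-dosing visit.

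The cost is SAP wording and programming, plus a few added tables. Some late AEs move to listings. Follow-up that a site never collected cannot be recovered, which is why follow-up time has to be shown.
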